# Clinical Trial Protocol

## Title

A Prospective Non-randomized Controlled Multi-center Study of Laparoscopic Intracorporeal Distal Rectal Transection by Using the Traditional Approach vs. Using Transanterior Obturator Nerve Gateway Approach for Ultralow Rectal Cancers

## NCT No.

Not assigned yet

## Date

2021/9/7

## **Trial sites**

Multi-center

## **Methodology**

Prospective, Non-randomized, Interventional, Controlled

*The Biomedical Research Ethics Committee of Peking University First Hospital* is overseeing the research. ([contact]; Email: [[contact]](mailto:[contact]); Address: [name])

## **Background**

Since 1992 when intersphincteric resection (ISR) for rectal cancer was first proposed by Braun et al, ISR has been widely used since it can significantly improve patients' quality of life by preserving the anus, especially for those with low rectal cancer. A series of studies have demonstrated its safety and feasibility. Standard laparoscopic ISR can not only ensure the radical resection of the tumor, but also preserve the anus.

Laparoscopic ISR with double stapling technique (DST) can provide a clearer view of the narrow pelvic and intersphincteric space, and the minimally invasive approach can relieve postoperative pain, shorten hospital stay, and generate better cosmetic outcomes compared with traditional combined abdominal perineal resection.

The wide application of ISR and DST has greatly improved the anal preservation rate for low rectal cancers, but the technical difficulty has also been obviously increased. In addition, for ultralow rectal cancers, because of the limited pelvic space, laparoscopic distal rectal transection could only be finished by multiple staplings resulting in an overlong stapling line, which could increase the risk for postoperative anastomotic leakage rate, which would seriously affect the patient's recovery and quality of life. Or the limited space could make it almost impossible to remove enough rectum to ensure a radical resection of the tumor, so distal rectal resection would have to be performed by converting to a transanal approach, that would definitely prolong the operative time and also increase the risk for anastomotic leakage. Although many scholars have tried to solve this problem, all the methods have failed to fundamentally solve the problem of "the oblique dissection" of the distal rectum for ultralow rectal cancers.

To solve the problem above, on the basis of a large number of ISR-DST performing experience, [name], the director of this clinical trial has explored a new distal rectal resection method-- transanterior obturator nerve gateway approach. This approach can conspicuously expand the pelvic space and optimize the dissection angle without significantly prolonging the operative time, thus reducing the technical difficulty. So, by using this method, it would be more likely to preserve the anus and reduce the possibility of converting to transanal approach without breach of tumor's radical resection. The purpose of this clinical trial is to prospectively collect and compare data on the patients' perioperative items and postoperative functional and oncological outcomes of this novel approach with the traditional approach, so as to confirm the safety and feasibility of this novel approach and its advantages over the traditional approach.

## Objective

To confirm the safety, feasibility and advantages by comparing the perioperative variables, postoperative functional and oncological outcomes of patients with ultralow rectal cancer treated by laparoscopic traditional distal rectal dissection vs. by transanterior obturator nerve gateway approach.

## Patients

Patients with ultralow ( $\leq 5$ cm from the anal verge) rectal cancer who are to undergo laparoscopic radical resection (ISR- DST) without any contraindications of general anesthesia, surgery or chemotherapy.

### ➤ Inclusion criteria

- 1) Age: 18-80 years old;
- 2) Pathologically diagnosed as rectal cancer with the lower margin of the tumor from the anal margin  $\leq 5$ cm;
- 3) CT, MRI or endoscopic ultrasonography: Single tumor, clinical T stage  $\leq 3$  or no invasion of the internal sphincter, maximum diameter  $\leq 10$ cm, no distant metastasis;
- 4) The patient or the patient-authorized representative completely understands the study protocol and voluntarily participates in this study, agrees to sign written informed consent.

### ➤ Exclusion criteria

- 1) The patient had previous abdominal surgery that will significantly infect the laparoscopic procedures;
- 2) Patients requiring emergency surgery owing to intestinal obstruction, perforation, or uncontrolled bleeding caused by tumor;
- 3) Patients with poor anal function preoperatively (Wexner score  $\geq 10$ );
- 4) ASA (American Society of Anesthesiologists) grading  $\geq IV$ ;
- 5) Pregnant patients;
- 6) Patients concomitant with severe mental illness;
- 7) The patient or the patient-authorized representative can't understand the contents and objectives of the study.

➤ **Withdraw criteria**

- 1) ISR cannot be performed by intraoperative evaluation and is replaced by Miles surgery;
- 2) Distant metastasis is confirmed intraoperatively or by postoperative pathological findings;
- 3) Patients had other primary tumors requiring surgical/drug treatment during the study, or had other illnesses that prevent the patient from continuing to participate this study;
- 4) Patients decide to withdraw from the study for any reason, or who are unable to complete the study because of any objective reasons.

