### **Sample size**

Two groups are designed, patients who are to receive the traditional approach to transect the distal rectum are assigned to the control group, patients who are to receive the transanterior obturator nerve gateway approach to transect the distal rectum are assigned to the experimental group. 100 cases are to be enrolled for the experimental group and not less than 100 cases are to be enrolled for the controlled group.

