- 4) Urethral catheterization will be routinely done preoperatively
- 5) If the patient refuses to accept the novel approach before surgery, they will be directly enrolled in the traditional group. If both approaches are acceptable to the patient, the decision whether to use the novel approach will be made according to the intraoperative

conditions (see operating procedures below).

- Operating procedures

General anesthesia; Modified lithotomy position (Fig. 1a); Establishment of pneumoperitoneum: Place a trocar 1cm above the umbilicus through which to establish pneumoperitoneum and keep the abdominal pressure as 12 mmHg (millimeters of mercury).

Trocar placement: above the umbilicus (trocar C, 10 mm), upper right and left quadrants (trocars B and D, 5 mm), lower right quadrant (trocar A, 12 mm), lower left quadrant (trocar E, 5 mm), the midpoint between the pubic symphysis and umbilicus (trocar F, 5 mm).

[figure not shown]

Fig.1 Patient position and trocar placement

Abdominal exploration: Explore the abdominal cavity in accordance with the principle of non-contact, from far to near step by step, explore the tumor finally.

The mesosigmoid and mesorectum are dissected from the right lateral rectum towards the root of the inferior mesenteric artery (IMA). The IMA is transected and ligated, so is the inferior mesenteric vein. Posterior space of the descending colon is dissected following opening the peritoneum beside the left rectum. The rectum in the pelvis is mobilized from posterior rectal space, anterior rectal space to bilateral rectal space successively. The lower edge of the tumor is marked by a clamp. The linear stapler is placed in the pelvis to clamp the distal rectum below the tumor to see if the transection can be done more than 1cm from the lower edge of the tumor. If yes, the distal rectum will be transected by the traditional approach (that means the patient will be assigned to the traditional group). The proximal bowel is transected through a small midline incision. Then the coloanal

anastomosis will be done intracorporeally. A surgical drain is placed in the pelvis and a terminal ileostomy is routinely performed. All incisions are closed.

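### Miles surgery decided after the transection approach is chosen leads to withdrawal and is counted in no outcome, so it can never count against that approach

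*Combined protocol and SAP*

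**What the plan says.** The withdrawal list, printed under Exclusion criteria, opens with the case in which "ISR cannot be performed by intraoperative evaluation and is replaced by Miles surgery". The Background names two expected benefits of the new approach: "it would be more likely to preserve the anus and reduce the possibility of converting to transanal approach". Only the second becomes an outcome.

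Under Primary outcomes, the conversion and leakage rates are each divided, per group, by the total number of cases enrolled. The available text does not say whether withdrawn patients belong to that total. Sample size says that "100 cases are to be enrolled for the experimental group", with at least as many controls, and does not mention withdrawals. Statistics names the tests but no analysis population.

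The Treatment section gives two routes into the groups. By the first, "If the patient refuses to accept the novel approach before surgery, they will be directly enrolled in the traditional group". By the second, a patient who accepts both approaches is assigned during the operation, when the stapler is tried below the tumor. If it can clear more than 1 cm, "that means the patient will be assigned to the traditional group"; if not, the patient joins the experimental group.

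**The concern.** Anus preservation is put forward as a benefit, and Miles surgery is the operation in which it is lost. The plan withdraws those patients and counts the event nowhere. If Miles surgery follows the choice of approach, it may say something about how that approach performed, yet the report would not show it. A reader could not tell whether one group preserved the anus more often. The conversion comparison would also omit any difference in Miles rates between the groups.

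**Working it through.** The plan gives no alpha, power, event rate or dropout for its 100 per group, so there is no figure of its own to reproduce. The check is first one of reading, then an illustration.

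**1. Where could Miles surgery be counted?**

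| Place in the protocol | Content bearing on this | Miles or anus preservation counted? |
|---|---|---|
| Treatment, variables recorded during the operation | Transanal conversion is the only failure item | No |
| Treatment, postoperative management | Catheter, drain, complications, pathology, hospital stay | No |
| Follow-up | Stoma closure time; Wexner score after closure | No; both presuppose a preserved anus |
| Primary outcomes | Angle, change in angle, distal margin, conversion, leakage | No |

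**2. Does the reading of the enrolled total matter?** If withdrawn patients are dropped, Miles cases leave numerator and denominator. If they are kept, they enlarge the denominator as patients without conversion or leak. Under neither reading is the Miles operation counted.

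**3. When is the decision made?** For a patient who accepts both approaches, a Miles decision before the stapler test precedes any choice of approach and leaves the patient without a group. A refuser is already in the traditional group when the same decision is made. Only decisions after the transection step is reached can bear on the approach in both groups alike.

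**4. How large could the effect be?** All rates are assumed; the documents give none. Take 100 patients per group reaching the transection step, with 5 transanal conversions in the experimental group and 15 in control. The difference is control minus experimental, with two-sided Fisher exact p and the Wald interval d ± 1.96·√[pE(1−pE)/nE + pC(1−pC)/nC].

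Base: 15.0% − 5.0% = 10.0 points; √(0.05·0.95/100 + 0.15·0.85/100) = 0.0418; interval 1.8 to 18.2; p = 0.032.

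*Conversion as the protocol defines it, withdrawn Miles cases dropped:*

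| Miles cases (experimental/control) | Rates | Difference (points) | p |
|---|---|---|---|
| 5/0 | 5/95 = 5.3% vs 15.0% | 9.7 | 0.033 |
| 0/5 | 5.0% vs 15/95 = 15.8% | 10.8 | 0.017 |
| 5/5 | 5.3% vs 15.8% | 10.5 | 0.031 |

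If they are kept, the difference stays at 10.0 points in every row.

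*Conversion or Miles surgery, a rate the protocol does not define:* difference = 10 + (Miles in control − Miles in experimental).

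| Miles cases (experimental/control) | Rates | Difference (95% CI) | p |
|---|---|---|---|
| 5/0 | 10% vs 15% | 5.0 (−4.1 to 14.1) | 0.39 |
| 3/2 | 8% vs 17% | 9.0 (−0.1 to 18.1) | 0.086 |
| 2/3 | 7% vs 18% | 11.0 (2.0 to 20.0) | 0.031 |
| 0/5 | 5% vs 20% | 15.0 (6.1 to 23.9) | 0.002 |
| 5/5 | 10% vs 20% | 10.0 (0.2 to 19.8) | 0.073 |

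The 5/0 and 0/5 rows are extremes. An equal split leaves the difference at 10.0 points.

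**5. Leakage.** With an assumed 9 leaks and 5 Miles cases in 100 patients, the rate is 9/100 = 9.0% per enrolled patient and 9/95 = 9.5% per anastomosis.

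**6. Why timing must limit any combined rate.** Suppose the five Miles decisions in the 0/5 row were all made in refusers before the transection step. Counted over everyone with a group, they would raise the difference from 10.0 to 15.0 points in favor of the new approach. Identical decisions in acceptors would count against nobody, because those patients had no group yet.

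**The case against.** The strongest reply is that Miles surgery here reflects operability, not the transection approach. The criterion asks whether ISR can be done at all, and both approaches are ways of transecting within ISR. Where pelvic space is limited, the Background says that "distal rectal resection would have to be performed by converting to a transanal approach", and that fallback is already a primary outcome. The operating procedures show no Miles branch after the stapler test. This stands for decisions made before the transection step, which should count against neither approach. It also makes later Miles cases plausibly rare. It does not show that there will be none, and the Background itself ties the approach to anus preservation.

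Second, the protocol's own rates hardly move. This stands. The larger shifts above come from an undefined rate with invented inputs, and the changes in p across 0.05 partly reflect a base case chosen close to it.

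Third, anus preservation appears in the Background but not in the Objective or among the primary outcomes, so the request is partly for an added outcome. This stands too, and it limits the severity.

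Fourth, the flow chart is not available in the text reviewed and might define enrolment or show withdrawals, and withdrawal reasons may be recorded anyway. Even so, a displayed withdrawal count would not be an outcome, and nothing in the available text asks for Miles surgery to be reported by group.

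A reader might infer that every Miles case is a hidden failure of an approach, or that the omission flatters the new one. The documents support neither. They give no Miles rate, and the two assignment routes allow an imbalance in either direction.

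**Conclusion.** The point holds in a limited form. As written, Miles surgery that follows the choice of transection approach is withdrawn and never counted against that approach, under either reading of the enrolled total. The anus-preservation benefit put forward in the Background therefore cannot be assessed from the planned outcomes.

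The number of such cases, and the direction and size of any bias, are unknown and may be zero. In the illustration, five Miles cases per 100 change the conversion difference by at most 0.8 points and leakage by about half a point. It would be wrong to conclude that the planned conversion or leakage results are materially distorted. What stays unseen is 1 point, per 100 patients in each group, for each Miles case by which one group exceeds the other. All these sizes rest on assumed rates. Severity is minor to should-fix.

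**What to change.** 1. Do not remove a patient from the perioperative analysis because of Miles surgery once the approach is chosen and the transection step is reached. Define the enrolled total under Primary outcomes accordingly.
2. Record Miles surgery (yes/no), whether the decision came before or after the stapler test or transection decision, and the assignment route (refusal or stapler test). Report it by group.
3. List Miles decisions made before the transection step separately, for refusers and acceptors alike, and count them against neither approach.
4. Keep transanal conversion as defined. Add one supportive rate of transanal conversion or Miles surgery, counting in both groups only Miles decisions made after the transection step is reached. State that it combines two different events and does not remove confounding by the stapler test.
5. Report leakage also per patient with an anastomosis.

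None of this alters a surgical decision. The cost is one definition, one data item with timing and route, a short list, one supportive analysis and a second leakage denominator. The study started on 2020-12-01, 280 days before the protocol date of 2021/9/7, so the item must be retrieved from operation records for cases since the start. Reported failure rates may look slightly less favorable.

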### **Sample size**

Two groups are designed, patients who are to receive the traditional approach to transect the distal rectum are assigned to the control group, patients who are to receive the transanterior obturator nerve gateway approach to transect the distal rectum are assigned to the experimental group. 100 cases are to be enrolled for the experimental group and not less than 100 cases are to be enrolled for the controlled group.

### **Treatment**

If the participant matches with the requirements for this study and agrees to take part in it, once hospitalized, the participant will complete the established preoperative tests including blood routine, the comprehensive metabolic panel, blood coagulation function, tumor markers, blood type, infectious disease screening tests, chest, abdominal and pelvic CT (Computed Tomography) scan and MRI, colonoscopy, echocardiogram, pulmonary function, venous duplex ultrasound of legs. All male patients will be routinely asked to fill

in the IIEF-5 sexual function scoring questionnaire preoperatively.

The following comprehensive treatment will be depended on the examination results:

➤ **Neoadjuvant therapy**

The treatment plan will be made in accordance with the NCCN (National Comprehensive Cancer Network) Guidelines for Diagnosis and Treatment of Colorectal Cancer (Version 1.2021).

Neoadjuvant chemoradiotherapy: Pelvis radiotherapy with a total dose of 50 Gy with 25 courses in 5 weeks. Neoadjuvant chemotherapy include single drug therapy: capecitabine (CAP, 1250 mg/m^2, BID) or double drug therapy: oxaliplatin combined with capecitabine (CapeOX, oxaliplatin 130 mg/m^2, day 1, capecitabine 1000mg/ m^2, day 1 ~ 14, then rest for 7 days, repeated every 3 weeks) or three-drug therapy (mFOLFOX6, oxaliplatin 85 mg/ m^2 intravenous infusion for 2 hours, leucovorin calcium 400 mg/m^2 intravenous infusion for 2 hours, 5-FU (fluorouracil) 400 mg/m^2 intravenous infusion for 1 day, Then 1200 mg/ m^2/d×2 days of continuous intravenous infusion with a total of 2400mg/m^2 for 46 ~ 48 hours, repeated every 2 weeks.

Abdominal and pelvic MRI and contrast enhanced CT will be routinely performed 6 to 8 weeks after neoadjuvant therapy to confirm the extent of tumor regression without new-found distant metastasis. Those whose clinical stage after neoadjuvant therapy changes from T4 to T3 will be seen as eligible in this study.

➤ **Surgical treatment**

● Preoperative preparation

- 1) Patients older than 60 years old or having a smoking history for over 10 years will receive lung ventilation training and atomization treatment for 3 days
- 2) Intestinal preparation will be done with oral cathartic medications 12-24 hours before surgery
- 3) Prophylactic antibiotics will be given once anesthesia is begun, the second antibiotics will be given if the operation lasts for over 3 hours
- 4) Urethral catheterization will be routinely done preoperatively
- 5) If the patient refuses to accept the novel approach before surgery, they will be directly enrolled in the traditional group. If both approaches are acceptable to the patient, the decision whether to use the novel approach will be made according to the intraoperative

conditions (see operating procedures below).

- Operating procedures

General anesthesia; Modified lithotomy position (Fig. 1a); Establishment of pneumoperitoneum: Place a trocar 1cm above the umbilicus through which to establish pneumoperitoneum and keep the abdominal pressure as 12 mmHg (millimeters of mercury).

Trocar placement: above the umbilicus (trocar C, 10 mm), upper right and left quadrants (trocars B and D, 5 mm), lower right quadrant (trocar A, 12 mm), lower left quadrant (trocar E, 5 mm), the midpoint between the pubic symphysis and umbilicus (trocar F, 5 mm).

[figure not shown]

Fig.1 Patient position and trocar placement

Abdominal exploration: Explore the abdominal cavity in accordance with the principle of non-contact, from far to near step by step, explore the tumor finally.

The mesosigmoid and mesorectum are dissected from the right lateral rectum towards the root of the inferior mesenteric artery (IMA). The IMA is transected and ligated, so is the inferior mesenteric vein. Posterior space of the descending colon is dissected following opening the peritoneum beside the left rectum. The rectum in the pelvis is mobilized from posterior rectal space, anterior rectal space to bilateral rectal space successively. The lower edge of the tumor is marked by a clamp. The linear stapler is placed in the pelvis to clamp the distal rectum below the tumor to see if the transection can be done more than 1cm from the lower edge of the tumor. If yes, the distal rectum will be transected by the traditional approach (that means the patient will be assigned to the traditional group). The proximal bowel is transected through a small midline incision. Then the coloanal

anastomosis will be done intracorporeally. A surgical drain is placed in the pelvis and a terminal ileostomy is routinely performed. All incisions are closed.

If the distal rectal transection cannot be done more than 1cm from the lower edge of the tumor, the anterior obturator nerve gateway approach will be used (that means the patient will be assigned to the experimental group). The steps are as follows: The peritoneum covering the ureter and external iliac artery is opened more than 2 cm across the vas deferens (male) or round ligament (female). The Retzius space and vesicohypogastric fascia are exposed. The obturator vessels and obturator nerve are properly identified. Care should be taken to avoid any injury when using energy devices near the obturator nerve. The gateway is then opened through the TME (total mesorectal excision) compartment and the lateral compartment. If necessary, an “endoloop” can be placed through the gateway, and the bundled S2-4 nerves, ureter and bladder vessels are gently retracted toward the cranial direction to widen the gap. The linear stapler is placed in the gateway to vertically transect the distal rectum. The following procedures are the same with the traditional group as described above.

During the operation, the following variables will be recorded: the angle between the linear stapler and the rectum, distance from the lower edge to the resecting margin, whether the operation converted to transanal approach, operative time, bleeding volume, anastomotic height from anal verge and the length of the stapling line.

➤ **Postoperative management:**

The following information will be recorded:

1) Vital signs (body temperature, pulse rate, respiration rate, blood pressure) are routinely monitored, gross volume of fluid input and output will be recorded every 24h, blood routine, the comprehensive metabolic panel and coagulation function tests will be performed every 3 days.

2) The time of catheter removal (days after operation), residual urine volume in the bladder will be measured by ultrasound examination. Whether there is a request to be re-catheterized or take oral medication to relieve the dysuria. All patients will be asked to fulfil the IPSS (International prostate symptom score) questionnaire to assess urinary function.

**Table 1.** International prostate symptom score assessing urinary function

In the past month:	Not at All	Less than 1 in 5	Less than Half the	About Half the	More than Half	Almost Always
--------------------	------------	------------------	--------------------	----------------	----------------	---------------

		Times	Time	Time	the Time	
1. Incomplete Emptying How often have you had the sensation of not emptying your bladder?	0	1	2	3	4	5
2. Frequency How often have you had to urinate less than every two hours?	0	1	2	3	4	5
3. Intermittency How often have you found you stopped and started again several times when you urinated?	0	1	2	3	4	5
4. Urgency How often have you found it difficult to postpone urination?	0	1	2	3	4	5
5. Weak Stream How often have you had a weak urinary stream?	0	1	2	3	4	5
6. Straining How often have you had to strain to start urination?	0	1	2	3	4	5
	None	1 Time	2 Times	3 Times	4 Times	5 Times
7. Nocturia How many times did you typically get up at night to urinate?	0	1	2	3	4	5
Total Score						

Score: 1-7: Mild 8-19: Moderate 20-35: Severe

- 3) The time of pelvic drain removal (days after operation)
- 4) Whether complicated with anastomotic leakage, ileus and long-lasting (more than 5 days) pulmonary or abdominal infection
- 5) All information of the pathologic report.
- 6) Postoperative hospital stay (days)

➤ **Postoperative chemoradiotherapy**

Radiotherapy program is the same with the neoadjuvant therapy. Chemotherapy will be advised for patients with stage II cancer accompanied with the following high-risk factors: histologically poorly differentiated with normal mismatched repair or stable microsatellite (MSS), pT4 (pathological stage T 4), vascular/nerve invasion, preoperative intestinal obstruction or perforation, ≤ 12 lymph nodes retrieved and R1 resection. The chemotherapy program is the same with neoadjuvant chemotherapy. If mismatch repair defect (dMMR) or high-level microsatellite instability (MSI-H) is confirmed by pathology, chemotherapy

will not be advised. Patients with stage III cancer will routinely receive chemotherapy.

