## Follow-up

1) Information on general medical history and physical examination will be collected every 3 months for 3 years

2) Blood tumor markers of CEA (carcinoembryonic antigen) and CA19-9 (carbohydrate antigen 19-9) will be tested every 3 months for 3 years

3) Abdominal and pelvic ultrasound and chest X-ray examinations will be carried out every 3 months for 3 years

4) Abdominal and pelvic MRI or contrast enhanced CT scan will be done every year for 3 years

5) Colonoscopy will be performed within 1 year after surgery. If there is any abnormality, reexamination will be required within half a year. If no abnormality is found, once a year for 3 years. All new-found adenomas by the colonoscopy during follow-up are recommended to be resected.

6) Sexual function score is assessed by filling in the questionnaire (IIEF-5) both preoperatively and 1 year later since operation.

**Table 2.** International Index of Erectile Function-5 assessing sexual function

Over the past 6 months:					
1. How do you rate your confidence that you could get and keep an erection?	Very low 1	Low 2	Moderate 3	High 4	Very high 5
2. When you had erections with sexual stimulation, how often were your erections hard enough for penetration?	Almost never/never 1	A few times (much less than half the time) 2	Sometimes (about half the time) 3	Most times (much more than half the time) 4	Almost always/always 5
3. During sexual intercourse, how often were you able to maintain your erection after you had penetrated (entered) your partner?	Almost never/never 1	A few times (much less than half the time) 2	Sometimes (about half the time) 3	Most times (much more than half the time) 4	Almost always/always 5
4. During sexual intercourse, how difficult was it to maintain your erection to completion of intercourse?	Extremely difficult 1	Very difficult 2	Difficult 3	Slightly difficult 4	Not difficult 5

5. When you attempted sexual intercourse, how often was it satisfactory for you?	Almost never/never 1	A few times (much less than half the time) 2	Sometimes (about half the time) 3	Most times (much more than half the time) 4	Almost always/always 5
IIEF-5 scoring:					

The IIEF-5 score is the sum of the ordinal responses to the 5 items.

22-25: No erectile dysfunction

17-21: Mild erectile dysfunction

12-16: Mild to moderate erectile dysfunction

8-11: Moderate erectile dysfunction

5-7: Severe erectile dysfunction

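### The IIEF-5 baseline is not fixed relative to neoadjuvant therapy, and the unadjusted 1-year comparison would mix any group difference in radiotherapy use or effect with the effect of the approach

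*Combined protocol and SAP*

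**What the plan says.** The opening paragraph of Treatment says that "once hospitalized, the participant will complete the established preoperative tests". The paragraph ends with the sexual function form: "All male patients will be routinely asked to fill" "in the IIEF-5 sexual function scoring questionnaire preoperatively" (one sentence, split by a page break). The next line reads "The following comprehensive treatment will be depended on the examination results", and neoadjuvant therapy is the first treatment described: "Pelvis radiotherapy with a total dose of 50 Gy with 25 courses in 5 weeks", with several chemotherapy options.

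On restaging, the plan says "Abdominal and pelvic MRI and contrast enhanced CT will be routinely performed 6 to 8 weeks after neoadjuvant therapy". No questionnaire is named at that visit. The same paragraph adds: "Those whose clinical stage after neoadjuvant therapy changes from T4 to T3 will be seen as eligible in this study".

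Follow-up, item 6, gives the whole IIEF-5 schedule: "Sexual function score is assessed by filling in the questionnaire (IIEF-5) both preoperatively and 1 year later since operation". Table 2 prints the form with a recall period of six months. The section on postoperative chemoradiotherapy allows radiotherapy after surgery on the same programme.

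Allocation is not random. Under Preoperative preparation and Operating procedures it follows either the patient's refusal of the new approach or whether the stapler can clamp more than 1 cm below the tumour. The Statistics section names the t test and the Mann-Whitney U test for quantitative data. It names no covariate or stratum and defines no IIEF-5 change score.

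**The concern.** A baseline for a surgical comparison should describe the patient as he comes to surgery, or at least be taken at the same stage of treatment in everyone. Here a single word, preoperative, can cover three situations: a man who goes straight to surgery and is scored shortly before it; a man scored at work-up who then receives pelvic radiotherapy; and a man who enters the study after down-staging and may be scored once radiotherapy is over. In the second case radiotherapy lies between his two scores, and the plan has no means of separating its effect from that of the operation.

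The Objective includes functional outcomes among the grounds for calling the new approach safe. That approach opens the lateral compartment and may involve retracting the S2-4 nerves, so sexual function is a natural place to look for harm, and the IIEF-5 is the only measure of it. If the groups differ in radiotherapy use or effect, the unadjusted comparison could show a harm that the approach did not cause, or hide one that it did.

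**Working it through.** **1. Order of events.** Read in printed order, Treatment runs: hospitalisation and work-up with the IIEF-5; treatment chosen from the results; neoadjuvant therapy where indicated; restaging by MRI and CT; surgery. The linking line makes treatment depend on the work-up, so the order is more than layout. For a man on this path, the baseline precedes restaging by at least 5 + 6 = 11 to 5 + 8 = 13 weeks, and surgery by longer.

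**2. Exception within the same section.** The work-up applies to a participant who already meets the requirements. A man who qualifies only once T4 has become T3 may have his study work-up, and so his IIEF-5, after radiotherapy. The timing is therefore not fixed, and it may differ among irradiated men.

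**3. Bias in the group comparison.** Let pE and pC be the shares of men in the experimental and control groups whose radiotherapy falls between the two scores, and LE and LC the mean IIEF-5 loss that it causes.

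Bias = pE × LE − pC × LC, which becomes L × (pE − pC) when the loss L is the same in both groups.

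If only 1-year scores are compared, with no change score, the same formula applies with p as the share irradiated at any time before the 1-year score.

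The documents state neither L nor the shares. Assuming L of 2, 3 or 5 points, equal in both groups:

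| Difference in share irradiated | L = 2 | L = 3 | L = 5 |
|---|---|---|---|
| 0 | 0 | 0 | 0 |
| 10 percentage points | 0.2 | 0.3 | 0.5 |
| 20 percentage points | 0.4 | 0.6 | 1.0 |

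For scale, the categories printed under Table 2 span 3 points (5-7), 4 points (8-11 and 22-25) or 5 points (12-16 and 17-21). The largest bias in the table, 1.0 point, is a third of the narrowest category.

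**4. Effect on the test.** Assume further an SD of 6 points and 60 men per group; neither figure is in the documents. Then se = 6 × √(2/60) = 1.095. With no true effect of the approach, the two-sided 5% test rejects with probability Φ(−1.96 − b/se) + Φ(−1.96 + b/se), where b is the bias:

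- equal shares, b = 0: 5.0%;
- 10-point difference, b = 0.2 to 0.5: 5.4% to 7.4%;
- 20-point difference, b = 0.4 to 1.0: 6.5% to 15.0%.

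**5. Within one group.** The mean change in a group contains p × L whatever happens in the other group. With half the men irradiated between scores, that is 0.5 × 2 = 1.0 to 0.5 × 5 = 2.5 points.

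**6. What a repeat score would achieve.** The form asks about the past six months, about 26 weeks. At restaging, 11 to 13 weeks after radiotherapy began, 26 − 13 = 13 to 26 − 11 = 15 weeks of that window still precede radiotherapy, which is half or slightly more. The repeat moves the baseline in the right direction but does not isolate the surgical effect.

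**The case against.** The strongest reply is that the protocol never says the score is taken before radiotherapy. Both places say only that it is preoperative, the tests are called preoperative tests, and a list that includes blood type, coagulation, echocardiogram and leg duplex also suits a surgical admission. This stands in part. A reader might infer that every irradiated man has a pre-radiotherapy baseline, and the text does not support that: the inference rests on the printed order, and the T4-to-T3 rule points the other way for some men. What remains is that the timing is left open and can vary.

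A reader might also infer that all sexual function lost to radiotherapy will be charged to the new approach. That goes too far. In the group comparison only a difference in radiotherapy use or effect produces bias; with equal shares and equal effect it is zero. Among patients who accept both approaches, allocation follows stapler reach and not stage, so an imbalance is possible but not shown. Even so, the Treatment section expects tumour regression from neoadjuvant therapy, and regression may bear on stapler reach, so balance cannot be presumed either. The direction is unknown.

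Third, radiotherapy affects the 1-year score whenever the baseline is taken, so moving the baseline is not the main remedy. This is right, and it sets the order of the fix. Finally, the IIEF-5 is not listed under Primary outcomes and is completed by men only, which limits the reach of the point.

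**Conclusion.** The point holds in a limited form. The plan does not fix the IIEF-5 baseline relative to neoadjuvant therapy, lists no repeat before surgery, and compares non-randomised groups by tests that take no account of radiotherapy. Any difference between groups in radiotherapy use or effect would therefore be mixed with the effect of the approach on a secondary, men-only outcome.

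The size rests on two assumed quantities, the loss due to radiotherapy and the imbalance in its use. Over the ranges shown the bias runs from nothing to 1.0 point. It is small against the printed categories, but could matter for a comparison meant to support a claim of safety. The documents do not show that the comparison will in fact be biased. The case for a change is that the exposure is avoidable at almost no cost.

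**What to change.** 1. **Statistics section.** Adjust or stratify the 1-year IIEF-5 comparison by preoperative pelvic radiotherapy (yes/no), with the baseline score as a covariate, and name which score serves as the baseline. Preoperative radiotherapy is given before the intraoperative allocation, so it is a proper adjustment variable. Postoperative radiotherapy comes after allocation; report it by group descriptively and do not use it as a main stratifier. This step needs only treatment records and also covers men already operated on.

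2. **Treatment, and Follow-up item 6.** State when the baseline IIEF-5 is taken relative to neoadjuvant therapy. For men given such therapy and not yet operated on, repeat the form at the existing restaging visit or at surgical admission, and keep the first score as the pre-treatment value.

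The cost is one extra five-item form at a visit that already takes place. Because of the six-month recall, the repeat reduces the mixing but does not remove it. It cannot be obtained for men already operated on.
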